7.1.4 Assessment of Potential Bias due to Treatment Group Assignment

VTL-308 is an open-label study. While every effort has been made in the study protocol to minimize the effects of post-treatment differences in investigator evaluation, medical care and subject behavior, there is a potential that differences in these factors may be associated with treatment group assignment, and that these differences might influence outcomes. An evaluation of the proportion of survivors at Study Days 28 and 91 will be carried out to determine whether these differences had any impact on study outcome. Parameters assessed will include, but not be limited to, the following:

- Alcohol use post-discharge. This will be evaluated based on either a PEth result of >20 ng/mL (evidence of moderate or heavy alcohol consumption) or any self-report of alcohol use post-discharge (note: a positive PEth result will supersede a self-report of no alcohol use);
- Length of Initial ICU Stay (<Median and ≥Median), defined as the first ICU discharge date minus ICU admission date plus 1, if the admission date is after randomization. If the admission date is before randomization, then the length of stay will be the discharge date minus randomization date plus 1. If the discharge date is missing and the subject died, the death date will be used;
- Length of Initial Hospital Stay (<Median and ≥Median), defined as the hospital discharge date minus randomization date plus 1. If discharge date is missing and the subject died, the death date will be used;
- Steroids Use Post-randomization (Yes/No);
- Steroids Use Post-randomization for <7 days (Yes/No);

- Steroids Use Post-randomization for ≥ 7 to < 14 days (Yes/No);
- Steroids Use Post-randomization for ≥ 14 to < 28 days (Yes/No);
- Steroids Use Post-randomization for at least 28 days (Yes/No);
- Concomitant heparin use within the first 10 days of the study (Yes/No);
- For the ELAD group only, ELAD treatment duration dichotomized based on < 72 hours vs. ≥ 72 hours. This analysis will be based on total ELAD treatment duration inclusive of any time off treatment (i.e., final stop date/time of treatment, defined as the time at which the ultrafiltrate pump is switched off for the last time – initial start date/time of treatment, defined as the time at which the ultrafiltrate pump is switched on for the first time). Additional analyses of ELAD treatment duration are described in [Section 8.2](#) and [8.10.1](#).

Post-randomization is defined as the steroid starting within one day after Randomization. If start dates are partial/missing for steroid use, the following imputation will be followed:

- If the entire set of steroid dates are partial, and only the year and month are reported, and they are the same year and month as the Randomization date, then the day will be imputed to be the same as the randomization day. If the first steroid date is a complete start date, and the following steroid records have partial dates that are in the same month and year, then all subsequent partial dates will be imputed to be the same as the first steroid date. Otherwise, the day will be imputed to the first day of the month;
- If the entire set of steroid dates are partial, and only the year is reported, and it is the same year as the randomization date, then the day and month will be imputed to be the same as the randomization day and month. If the first steroid date is a complete start date, and the following steroid records have partial dates in the same year, then all subsequent partial dates will be imputed to be the same as the first steroid date. Otherwise, the day and month will be imputed to January 1st;
- If the entire set of steroid dates are completely missing, then the start dates will be imputed to be the same as the randomization date.

The same logic will be applied for steroid end dates, using discontinuation dates instead of randomization dates. If the steroid is ongoing, the last visit date for the subject will be used.

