4.3 INCLUSION CRITERIA

Subjects must meet ALL inclusion criteria to be eligible for the study:

1. Age ≥ 18 ;
2. Total bilirubin ≥ 16 mg/dL (≥ 273.6 $\mu\text{mol/L}$);
3. A clinical diagnosis of alcohol-induced liver decompensation (AILD), based upon lab test or medical history or family interview with a causal relationship and temporal association (6 weeks or less) of alcohol use and hospital admission for this episode of AILD;
4. Maddrey score ≥ 32 ;
5. Subjects must have AILD that is severe acute alcoholic hepatitis (sAAH) diagnosed with either:
 - a. A confirmatory liver biopsy, OR
 - b. Two or more of the following:
 - i. Hepatomegaly,
 - ii. AST > ALT,
 - iii. Ascites,
 - iv. Leukocytosis (WBC count above lab normal at site);

Note: Subjects will be classified as either:

- a. AILD that is sAAH with **no** underlying liver disease other than alcoholic liver disease, OR
 - b. AILD that is sAAH **with** evidence of underlying liver disease other than alcoholic liver disease which must be documented by:
 - i. Liver biopsy, AND/OR
 - ii. Laboratory findings, AND/OR
 - iii. Medical history;
6. Not eligible for liver transplant during this hospitalization;
 7. Subject or legally-authorized representative must provide Informed Consent;
 8. Subject must be eligible for Standard of Care treatment as defined in the protocol.

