5.5.6 Evaluations at Discharge

In addition to the daily labs above, on the date of discharge the following should also be performed:

- PEth test for alcohol use
- Discharge Dietary consult, including weight (within 24 hours prior to discharge); follow-up Dietary consult (including weight) with each return study visit
- EQ-5D-5L Quality of Life (QOL) questionnaire (within 24 hours prior to discharge)

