The study site will notify the home visit agency at the time of subject discharge (i.e., at a minimum provide subject's name, address, contact information). The Investigator will provide the discharge orders for the home visits to commence. If the subject is discharged to a skilled nursing facility (SNF), hospice, or rehabilitation facility, the Investigator will assure discharge orders are reflective of the research to be carried out in the facility by the home visit practitioner. It is the study site's responsibility to ensure the home visit will be allowed at the facility. In both cases, discharge to home or to another facility, every effort will be made by the home visit practitioner to schedule the initial visit within one week of hospital discharge. Subsequent visits will be scheduled weekly (± 2 days) thereafter through the End of Study Day 91 (based on the original date of discharge not on the day of the previous visit). All study subjects must have a valid home address and phone number where they can be reached, or the information of the facility to which they are to be transferred.

The initial home visit will be scheduled for 1 to 2 hours; subsequent visits will be scheduled for approximately 1 hour. During the visits, the home visit practitioner will administer two questionnaires and collect an alcohol biochemical marker, PEth blood spot test ([Center for Substance Abuse Treatment 2006](#); [Allen 2003](#); [Cluver 2007](#); [Miller 2005](#)). The home visit practitioner's scope of practice does not extend past the aforementioned duties. During the visit if the home visit practitioner, in his/her professional opinion, deems the subject in need of immediate medical attention, the home visit practitioner will observe his/her specific agency protocol as appropriate and notify the Principal Investigator and/or appropriate healthcare provider within 24 hours of the event. Again, as with the Blinded Investigator, the home visit personnel are not to be informed of the subject's treatment group. This must be reinforced with the subjects at discharge.

Initial Weekly Visit (1 to 2 hours)

- Alcohol Timeline Followback Questionnaire (TLFB)
- Modified Treatment Services Review Questionnaire (mTSR)
- Test for alcohol use (PEth)

Subsequent Weekly Visits through End of Study Day 91 (irrespective of scheduled Study Day Evaluations) (1 hour)

- Alcohol Timeline Followback Questionnaire (TLFB)
- Modified Treatment Services Review Questionnaire (mTSR)

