8.9 HOME HEALTH CARE SUMMARY

After hospital discharge, home visits are conducted on a weekly basis up to Study Day 91 for all subjects to administer questionnaires on self-reported alcohol use and treatment services utilization, along with collection of an alcohol biomarker (PEth test). The proportion of subjects consuming alcohol post-discharge will be summarized by treatment group based on the following criteria:

- Subjects who reported any standard drink taken at any time post-hospital discharge;
- Subjects with a PEth lab results >20 ng at any time post-hospital discharge.

In order to evaluate differences between the treatment groups on the above recidivism variables, a Chi-squared test will be performed.

All home health care summary data will be listed.

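### The post-discharge drinking variable applies a fixed PEth cut-off of 20 ng/mL without using the screening or discharge PEth, so it cannot separate residual PEth from new drinking

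*SAP*

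**What the plan says.** SAP 7.1.4, which assesses bias from open-label assignment, defines alcohol use after discharge by "either a PEth result of >20 ng/mL (evidence of moderate or heavy alcohol consumption) or any self-report of alcohol use post-discharge". Where the two sources disagree, "a positive PEth result will supersede a self-report of no alcohol use". Survival at Study Days 28 and 91 is then examined by this variable.

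SAP 8.9 has two separate lines: "Subjects who reported any standard drink taken at any time post-hospital discharge" and "Subjects with a PEth lab results >20 ng at any time post-hospital discharge". The second gives the unit as ng; I read it as ng/mL, as in 7.1.4. It continues: "In order to evaluate differences between the treatment groups on the above recidivism variables, a Chi-squared test will be performed". The override of self-report appears only in 7.1.4.

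The protocol collects PEth at three stages:
- at screening, within 24 hours before randomization, to show whether the subject has been drinking (5.2.3 and 5.2.3.1);
- on the date of discharge, where 5.5.6 lists "PEth test for alcohol use";
- at home, where the agency tries to "schedule the initial visit within one week of hospital discharge" and then visits weekly to Study Day 91 (5.5.7).

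Entry requires a "temporal association (6 weeks or less) of alcohol use and hospital admission" (Protocol 4.3).

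**The concern.** Subjects are selected for recent alcohol use, and the protocol itself treats a PEth taken in hospital as evidence of earlier drinking. The marker is therefore expected to outlast intake to some extent. A home sample above 20 may reflect drinking since discharge, drinking before admission, or both. The SAP assigns it to the period after discharge in every case. A subject whose PEth is falling and who reports abstinence is still recorded in 7.1.4 as a post-discharge drinker.

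The variable serves the open-label bias check and a between-arm test of relapse. If residual PEth is common at the first home visits, two things follow. The drinking group contains abstainers, which blurs any relation between drinking and survival. The false positives also depend on the time from last drink to first home sample, and hence on length of stay, which may differ by arm.

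**Working it through.** The plan gives no figure to reproduce; 20 ng/mL is a definition. The documents state no PEth half-life, detection window or expected level, so the half-lives and starting levels below are **assumptions**.

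**Step 1. The rule as written.** Suppose PEth is 300 at discharge and 150 a week later (one 7-day half-life: 300 × 1/2), and the subject reports abstinence. Under 7.1.4 the result is above 20, so PEth overrides the report and the subject is a drinker. Under 8.9 the subject counts on the PEth line but not on the self-report line. Neither section looks at the 300.

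**Step 2. Days above 20 after the last drink, with no further drinking.** Assuming first-order decay, days = half-life × log2(C0/20), where C0 is the level at the last drink. The values of log2(C0/20) are 4.64, 5.64 and 6.64 for C0 = 500, 1,000 and 2,000.

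| Half-life | C0 500 | C0 1,000 | C0 2,000 |
|---|---|---|---|
| 2 days | 9.3 | 11.3 | 13.3 |
| 4 days | 18.6 | 22.6 | 26.6 |
| 7 days | 32.5 | 39.5 | 46.5 |
| 10 days | 46.4 | 56.4 | 66.4 |

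For half-lives of 4 to 10 days the range is about 19 to 66 days. At 2 days it stays under two weeks even from 2,000.

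**Step 3. Level at a given day after the last drink.** Level = C0 × 2^(−d/half-life), with C0 = 1,000.

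| Day d | Half-life 4 | Half-life 7 | Half-life 10 |
|---|---|---|---|
| 21 | 26 | 125 | 233 |
| 28 | 8 | 62 | 144 |
| 42 | 0.7 | 16 | 54 |

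At day 21 all three are positive, at day 28 two are, and at day 42 one is. Day 42 matters because the entry criterion allows the last drink up to 6 weeks before admission; for a subject at that limit, the day-42 row describes the level on admission.

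**Step 4. Screening level needed to be above 20 at the first home sample.** Level = 20 × 2^(T/half-life), with T counted from screening. Discharge on day 7 plus one week gives T = 14.

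| T | Half-life 2 | Half-life 4 | Half-life 6 | Half-life 10 |
|---|---|---|---|---|
| 14 | 2,560 | 226 | 101 | 53 |
| 28 | 327,680 | 2,560 | 508 | 139 |

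The level needed rises with T for every half-life. Where residual PEth is present, earlier discharge therefore gives more false positives. That direction follows from decay alone; the amount does not.

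**Step 5. By arm.** ELAD subjects wait for treatment and then have at least 72 hours of it unless stopped early. Protocol 5.5.1 foresees discharge before the end of Study Day 7, and SAP 3.3 mentions Controls discharged within 72 hours. Longer ELAD stays are plausible, but length of stay by arm is not given, so no arm difference in false positives can be computed.

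**The case against.** **The persistence of PEth is not in the documents.** This stands. A reader might infer that relapse is over-counted as a matter of fact. The documents do not support that: it depends on half-life, starting level and time since last drink. What they do show is that the rule cannot tell the two sources apart.

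**The arm bias is speculative.** This largely stands. A reader might suppose that Controls go straight home and are therefore labelled drinkers more often. The plan gives Controls a safety check at the end of Study Day 2, and entry requires bilirubin of at least 16 mg/dL and a Maddrey score of at least 32. Subjects discharged earlier also have more weekly samples and more real time in which to drink, so a higher positive rate among them would not be all residual.

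**The SAP already mitigates the problem.** Partly so. Section 8.9 tabulates self-report separately and lists all home health data, and 7.1.4 also examines length of hospital stay. But listings do not change the derived variable, and in 7.1.4 the two sources are merged with PEth prevailing.

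**Requiring a rise in PEth would be worse.** This stands against a rise-only rule. A subject discharged at 300 who drinks steadily and reads 300 every week never rises and never drops to 20, so would be missed, and PEth could no longer contradict a denial. The correction must therefore count values that fail to fall.

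**Conclusion.** The gap is real and follows from the text: a fixed cut-off, no washout and no reference to an earlier sample, although screening and discharge samples exist. Over-counting of relapse is a conditional risk. It could affect home samples for several weeks after the last drink if the half-life is about 4 days or more and the starting level is several hundred ng/mL or higher. It is small or absent if the half-life is about 2 days or the last drink was long before admission. Neither the share of subjects affected nor a between-arm effect can be derived from the documents.

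The consequence is confined to supportive analyses. The primary log-rank test and the secondary endpoints (survival proportions at Days 28 and 91, and bilirubin response at Day 7) do not use PEth. The change is still worth making, because this variable is part of the plan's check on whether behaviour after discharge differed by arm.

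**What to change.** In SAP 7.1.4 and 8.9, add a carry-over-corrected definition. Count a PEth result as post-discharge drinking when it is above 20 ng/mL and either:

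- (a) it has not fallen from the immediately preceding PEth by more than a prespecified assay variation, so that flat and rising values count; for the first home sample the reference is the discharge value, or screening if discharge is missing; or
- (b) it follows an earlier value at or below 20.

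Under this definition, let PEth override reported abstinence only in (a) or (b), and keep any self-reported drinking as positive. Report the existing any-above-20 rule alongside, and give the unit in 8.9 as ng/mL.

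The cost is a SAP derivation; every sample is already collected. Two limits should be stated. Drinking that only slows the decline will be caught only by the weekly questionnaire or the retained count. Also, a first home sample soon after discharge may show little fall even with abstinence: at a 10-day half-life the fall is 1 − 2^(−0.2) = 13% over 2 days, against 1 − 2^(−0.7) = 38% over 7 days. The SAP should say how close two samples may be before an earlier one serves as the reference.

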7.3.1 Transplant-Free Survival

Typically, orthotopic liver transplantation would not take place in patients diagnosed with sAH until the patient has demonstrated at least 6 months of abstinence. However, recent data ([Burra et al. 2010](#)) has suggested that outcomes from liver transplant in sAH patients are at least as good, and in some analyses better, than outcomes for subjects with viral hepatitis or other conditions associated with liver transplantation. In order to accommodate any potential imbalance between transplant rates in the ELAD-treated and Control subjects in the VTL-308 study, transplant-free survival (TFS) will be assessed as an exploratory efficacy analysis.

TFS will be assessed using a log-rank analysis of survival as with the primary efficacy endpoint, using the ITT population. However, unlike the primary efficacy analysis, subjects receiving a transplant will be treated as follows:

- Censored in the analysis at the time of transplant and be dealt with as though they had dropped out of the study following transplant;
- Included in the analysis as an event at the date/time of the transplant (i.e., transplant-free survival).

In addition an analysis will be carried out of the proportion of transplant-free survivors at Study Day 91 using the ITT population. For this analysis, subjects receiving a transplant will either:

- Not be included in either the denominator or the numerator of the calculation of the proportion of survivors (i.e. they will be dealt with as though they had dropped out of the study prior to Study Day 91);
- Counted in the analysis as an event.

7.3.2 Proportion of Survivors at Study Day 28 and 91

The proportion of survivors at Study Day 28 and at Study Day 91 for ELAD-treated subjects will be provided for the following subgroups:

- ELAD treatment duration based on PERF data, defined as total hours during which the ultrafiltrate pump is on (<72 hours vs. ≥72 hours);
- Total amount of ultrafiltrate delivered (dichotomized based on median value);
- Total amount of oxygen utilization by the cell cartridges (dichotomized based on median value);

- Total number of ELAD components exchanged and total number of exchanges for specific components (e.g. UFGs, bubble traps, etc.) (dichotomized based on median value);
- Total blood loss estimated for each subject based on component exchange (dichotomized based on median value).

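### SAP 7.1.4 compares Day-28 and Day-91 survival across steroid-duration bands that death itself cuts short, so a survival difference appears with no steroid effect; stay and ELAD-duration splits need a caveat

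*SAP*

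**What the plan says.** SAP 7.1.4 acknowledges that care and behavior after treatment may differ by arm in an open-label trial. It then plans a check: "An evaluation of the proportion of survivors at Study Days 28 and 91 will be carried out", with the aim "to determine whether these differences had any impact on study outcome". Ten parameters are listed. Seven are observed durations:

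- **Steroids, four bands:** under 7 days, 7 to under 14, 14 to under 28, and "Steroids Use Post-randomization for at least 28 days (Yes/No". On the start of the clock: "Post-randomization is defined as the steroid starting within one day after Randomization". On its end: "If the steroid is ongoing, the last visit date for the subject will be used".
- **Initial ICU stay,** split at the median: "If the discharge date is missing and the subject died, the death date will be used".
- **Initial hospital stay,** split at the median: "If discharge date is missing and the subject died, the death date will be used".
- **ELAD duration,** under 72 hours or longer, ELAD arm only.

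The other three are alcohol use after discharge, any steroid use, and heparin within the first 10 days.

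SAP 7.3.2 repeats the ELAD split on pump time: "ELAD treatment duration based on PERF data, defined as total hours during which the ultrafiltrate pump is on (<72 hours vs. ≥72 hours". Neither section has a landmark, a time-dependent covariate, an exclusion of early deaths or a caution on interpretation. Elsewhere the SAP does set early deaths aside: 7.2.2 (bilirubin change), 7.3.5 (Lille score) and 7.3.7 (infection, fluid and bleeding events).

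**The concern.** A duration that ends at death is partly a measure of survival. Tabulating survival against it builds in an association (immortal-time bias) whether or not the exposure does anything. For steroids the direction is fixed: early deaths must fall in the shorter bands and cannot fall in the longest.

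Two wrong conclusions could follow. Long steroid courses could look protective. And if ELAD does prolong life, more ELAD subjects will reach the long bands simply by living, which would look like an imbalance in care. Protocol 7.3.1 promised that the SAP would examine differences in steroid administration between the groups and set out how to handle them, so this table is likely to be relied on.

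**Working it through.** **Inputs.** Control hazard λ = 0.004 per day and hazard ratio 0.4, hence 0.0016 for ELAD (protocol 7.1). One-year Control survival 40% to 48% (SAP 1.3), which if exponential gives −ln(0.40)/365 = 0.0025 and −ln(0.48)/365 = 0.0020 per day. N = 150, 1:1. The share f of subjects intended for at least 28 days of steroids is not in the documents; 30%, 50% and 70% are assumed.

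**Anchor.** SAP 7.1.4 states no figure of its own. The hazards reproduce the protocol's medians: ln 2/0.004 = 173 days and ln 2/0.0016 = 433 days, against 175 and 438 stated.

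**Steroid bands, no steroid effect.** Let S28 = exp(−28λ). Everyone in the 28-day band is alive at about Day 28. The remainder holds those intended for less, plus those intended for 28 days who died first:

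survival in the remainder = (1−f)·S28 / [(1−f) + f·(1−S28)]

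At λ = 0.004, S28 = exp(−0.112) = 0.894:

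| f | Remainder | 28-day band | False gap |
|---|---|---|---|
| 0.3 | 0.6258/0.7318 = 85.5% | 100% | 14.5 points |
| 0.5 | 0.4470/0.5530 = 80.8% | 100% | 19.2 points |
| 0.7 | 0.2682/0.3742 = 71.7% | 100% | 28.3 points |

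As f approaches 0 the gap approaches 1 − 0.894 = 10.6 points, its minimum at this hazard. At 0.0025 per day the minimum is 1 − exp(−0.07) = 6.8 points, and the gap is 9 to 20 points over the same f.

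**Effect on an ELAD versus Control comparison within bands.** At hazard ratio 0.4, true Day-28 survival is exp(−0.0448) = 95.6% against 89.4%, a difference of 6.2 points. In the 28-day band both arms show about 100%, so no difference can appear. In the remainder with f = 0.5 in both arms, ELAD is 0.4781/0.5219 = 91.6% against 80.8%, a difference of 10.8 points. Neither stratum returns 6.2.

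**Simulation under the null** (exponential survival; assumed intended mix 10/35/15/40% across the four bands; λ = 0.004). Day-91 survival is 77.7% in the 28-day band and 64.9% in the rest. SAP 7.1.4 names no test; a chi-square at N = 150 would reject in 99.5% of trials at Day 28 and 38.6% at Day 91, against a nominal 5%. With a Day-28 landmark, Day-91 survival is 77.7% in both groups and rejection falls to 5.4%.

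**Hospital stay** (λ = 0.004). If discharge is independent of death with median 14 days, shorter versus longer stays give 84.5% vs 94.3% at Day 28 and 65.7% vs 73.4% at Day 91. If sicker subjects stay longer, the Day-91 comparison can reverse, for example 82.3% vs 66.4%.

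**ELAD under 72 hours.** Expected deaths within 3 days per 75 subjects: 75·[1 − exp(−0.0048)] = 0.4 to 75·[1 − exp(−0.012)] = 0.9.

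**Deaths lost to a Day-28 landmark** (75 per arm). By Day 28: 75·(0.106 + 0.044) ≈ 11. By Day 91: 75·(0.305 + 0.136) ≈ 33.

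**The case against.** The strongest reply is that a reader might infer too much from this defect, in four ways.

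- **That the SAP has no other check on care differences.** It has several: 1.2.3 (objectives), 4.3 with Appendix A (standard-of-care compliance by arm), 7.3.3 (survival by steroid, pentoxifylline and N-acetylcysteine use), 8.4 (medications by period), 8.8 (hospitalization) and 8.9 (alcohol). Most do not condition on a duration that depends on survival.
- **That long stays will look protective by construction.** They need not. Well subjects discharged early also fall below the median, and the death date is used only when a discharge date is missing.
- **That death drives the ELAD 72-hour split.** Under one subject per 75 is moved at the protocol hazards. The listed discontinuation criteria (adverse events, DIC, need for hemodialysis) are probably the larger problem. The split is within the ELAD arm, so it cannot speak to bias between arms at all.
- **That the whole of 7.1.4 is unreadable.** Any steroid use and early heparin are largely unaffected. Post-discharge alcohol use is not a duration, though it does require living to discharge.

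All four limits stand. It is also fair that the larger gaps need a high f, which the documents do not support: protocol 5.4.1.2 reassesses at 7 days and counts steroid treatment given before admission. That changes the size of the gap, not its existence, since the 10.6-point floor at 0.004 per day holds for any f. A landmark also leaves confounding, because the same section stops steroids in non-responders. None of this repairs the steroid bands.

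**Conclusion.** The point holds for the four steroid-duration bands. The 28-day band is about 100% alive at Day 28 by definition, and with no steroid effect the false gap is at least about 10.6 points at 0.004 per day, or 14 to 28 points if 30% to 70% of subjects are intended for 28 days. The sizes rest on exponential survival and an assumed share or mix; the direction and the 100% do not.

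For ICU and hospital stay, the tables are distorted in an unknown direction. For ELAD duration, death plays a minor part and confounding by deterioration probably a larger one.

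A reader might go on to doubt the main result. The documents give no ground for that here: the primary log-rank comparison in the ITT population uses none of these groupings. What is at risk is the conclusion drawn about open-label bias and about ELAD duration and outcome.

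**What to change.** In SAP 7.1.4:

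1. Classify steroid duration and initial ICU and hospital stay at a Study Day 28 landmark, among subjects alive then, and compare survival from Day 28 to Day 91 by arm. Define the top steroid band as use continuing to the landmark, so that a course begun the day after randomization is not misplaced. Alternatively, enter these exposures as time-dependent covariates in the OS Cox model, which keeps the early deaths.
2. Drop Day-28 survival tables for any exposure still accruing at Day 28.
3. For ELAD duration, here and in 7.3.2, use an early landmark such as End of Study Day 7.
4. State that these tables are descriptive and remain confounded by indication: steroids stop in non-responders and ELAD stops for deterioration.

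The cost is SAP wording and table programming, with no new data. The real loss is information: a Day-28 landmark leaves out about 11 of 33 expected Day-91 deaths (one third), including the acute-phase deaths most relevant to ICU care. That is a reason to run the time-dependent model as well.
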